8.2.2 Period of Assessment

All AEs that occur from the time the informed consent is signed through Day 28 will be documented, recorded, and reported. After the end of the protocol-defined AE reporting period, sites must report to the safety office serious, unexpected, clinically suspected adverse drug reactions if the study site staff becomes aware of the event on a passive basis.

8.2.3 Assessment of Adverse Event

The Investigator will evaluate all AEs with respect to **Seriousness** (criteria listed above), **Severity** (grading), and **Causality** (relationship to study agent and relationship to research) according to the following guidelines.

8.2.3.1 Severity

The Investigator will grade the severity of each AE according to the “DAIDS (Division of AIDS) Table for Grading the Severity of Adult and Pediatric Adverse Events” Version 1.0, December, 2004: (Clarification August 2009) which can be found at: http://rsc.tech-res.com/Document/safetyandpharmacovigilance/Table_for_Grading_Severity_of_Adult_Pediatric_Adverse_Events.pdf

8.2.3.2 Causality of Adverse Event to the Intervention

Causality (likelihood that the event is related to the study agent) will be assessed considering the factors listed under the following categories:

Definitely Related

- reasonable temporal relationship
- follows a known response pattern
- clear evidence to suggest a causal relationship
- there is no alternative etiology

Probably Related

- reasonable temporal relationship

- follows a suspected response pattern (based on similar agents)
- no evidence of a more likely alternative etiology

Possibly Related

- reasonable temporal relationship
- little evidence for a more likely alternative etiology

Unlikely Related

- does not have a reasonable temporal relationship
- OR
- good evidence for a more likely alternative etiology

Not Related

- does not have a temporal relationship
- OR
- definitely due to an alternative etiology

Other factors (e.g., dechallenge, rechallenge) should also be considered for each causality category when appropriate. Causality assessment is based on available information at the time of the assessment of the AE. The investigator may revise the causality assessment as additional information becomes available.

8.2.4 Investigator Documentation of Adverse Event

The severity of the AE will be recorded in an appropriate source document. AEs (per the definition above) and SAEs will be recorded in the appropriate section of the AE electronic case report forms (eCRF) and entered into a database for IRB/IEC review and FDA/COFEPRIS reporting requirements.

8.3 Investigator Reporting Responsibilities to the Sponsor

8.3.1 Serious Adverse Events

SAEs (whether or not they are also UPs) must be reported on the SAE/UP Report Form and sent to the Sponsor Clinical Safety Office (CSO) by fax or e-mail attachment. Deaths and immediately life threatening SAEs must be reported within 1 business day after the site becomes aware of the event. All other SAEs must be reported within 3 business days of site awareness.

SPONSOR CLINICAL SAFETY OFFICE CONTACT INFORMATION:

OCRPRO Clinical Safety Office
[name]
[name]

[contact]
[contact]

E-mail: [contact]

8.3.2 Unanticipated Problems

Non-Serious AEs that are UPs must also be reported on the SAE/UP Report Form and sent to the CSO by fax or e-mail attachment no later than 7 calendar days of site awareness of the event. The UPs that are not AEs are not reported to the Sponsor CSO.

8.3.3 Pregnancy

Pregnancy itself is not an AE. However, complications of pregnancies are AEs and may be SAEs. Pertinent obstetrical information for all pregnancies will be reported to the CSO via fax or email within 3 business days from site awareness of the pregnancy.

Pregnancy outcome data (e.g., delivery outcome, spontaneous or elective termination of the pregnancy) will be reported to the CSO within 3 business days of the site's awareness on a protocol-specified form.

The procedures that should be followed in the event of a pregnancy include:

- Discontinuation of the study agent
- Unblind per the unblinding section of the protocol
- Pregnancies that do not result in SAEs will be reported to the IRB/IEC in summary format with the continuing review or according to the local IRB/IEC requirements
- Advise research subject to notify the obstetrician of study agent exposure

Additionally the protocol team will report the pregnancy to the DSMB.

8.4 Investigator Reporting Responsibilities to the Site IRB/EC

8.4.1 IND safety reports

Investigators are responsible for submitting IND Safety Reports and UP summaries that are received from the IND Sponsor to their local IRB/Ethics Committee. Investigators must also comply with all local IRB/Ethics Committee reporting requirements.

8.4.2 Expedited Reporting to the Site IRB/EC

Unanticipated problems that are either AEs or non-AEs, (as defined above) and protocol violations which do not meet the definition of a UP will be reported within 7 calendar days of investigator awareness (or as required by the site IRB/EC).

8.4.3 Annual Reporting to the IRB/EC

In addition to each IRB/EC yearly reporting requirements, the following items will be reported to the IRB/EC in summary at the time of Continuing Review (or more frequently as required by the site IRB/ECs):

- All unanticipated problems

- All protocol deviations which in the opinion of the investigator should be reported according to the site's IRB/EC reporting guidelines
- Summaries of all AEs

8.5 Follow-up of Adverse Events and Serious Adverse Events

AEs that occur following enrollment of the subject (by signing the informed consent) are followed until the final outcome is known or until the end of the study follow-up period (Study Day 28).

SAEs that have not resolved by the end of the follow-up period are followed until final outcome is known. If it is not possible to obtain a final outcome for an SAE (e.g., the subject is lost to follow-up), the reason a final outcome could not be obtained will be recorded by the investigator on the AE CRF (if the CRF is still open) and the SAE/UP Report Form.

SAEs that occur after the study follow-up period that are reported to and are assessed by the Investigator to be possibly, probably, or definitely related must be reported to the CSO, as described above.

8.6 Sponsor's Reporting Responsibilities

Serious and unexpected suspected adverse reactions (SUSARs) as defined in 21 CFR 312.32 and determined by the IND Sponsor will be reported to US FDA and all participating Investigators as IND Safety Reports.

The IND Sponsor will submit an Annual Report of the progress of the investigation to the US FDA and Mexico COFEPRIS as required.

AEs that are also UPs will be summarized by the IND Sponsor and distributed to Investigators.

8.7 Safety Monitoring

8.7.1 Investigator Safety Monitoring

Investigators participating in this clinical trial are responsible for:

- Protecting the safety and welfare of subjects
- Evaluating subject safety, including physician assessment of AEs for seriousness, severity, and causality
- Notifying the sponsor of SAEs and immediately-reportable events (per 8.3)
- Providing detailed written reports, including confirmatory tests promptly following immediate initial reports
- Informing the IRB/IEC of SAEs as required by applicable regulatory requirements

8.7.2 Protocol Team Monitoring

The protocol team will review the enrollment and study-related safety data (AEs and SAEs) from all sites periodically during the study. These reviews will occur at a minimum twice monthly during active enrollment and follow-up.

8.7.3 Sponsor Medical Monitor

A Medical Monitor, representing the IND Sponsor, has been appointed for oversight of safety in this clinical study. The Sponsor Medical Monitor will be responsible for performing safety assessments as outlined in a Safety Review and Communications Plan (SRCP) (see Section 8.7.6).

8.7.4 Pausing Rules

The following automatic pausing rules to suspend study drug administration are in place for this study:

- 2 (or more) subjects experience the same Grade 4 AE and/or SAE that is unexpected and possibly, probably, or definitely related to the study drugs OR
- 4 (or more) subjects experience the same Grade 3 or higher AE that is unexpected and possibly, probably, or definitely related to the study drugs
- If any of pausing rules are triggered, the following will occur:
 - The Sponsor's Medical Monitor will undertake a review of cumulative AE data within 72 hours of being made aware of the events specified above, AND
 - The DSMB will be notified of the above Medical Monitor review, and of the Medical Monitor's findings.
- If the Medical Monitor is unable to complete the review of the safety data within 72 hours of awareness by the Clinical Safety Office, study enrollment will be halted until the review can take place. The DSMB will again be notified of any such review, and of the findings of the Sponsor's Medical Monitor. In the event of a study pause, after the above appropriate review, the sponsor in consultation with the Sponsor's Medical Monitor may allow enrollment or ask the DSMB for a review of the safety data.
- The IND Sponsor, in collaboration with the PI, may also pause for an individual subject or entire group if a safety concern is identified during routine aggregate data analysis.

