3.4 Overview of Study Design

The study will be a multicenter, randomized, double-blind, placebo controlled trial to evaluate the efficacy of NTZ+ SOC compared to PCB + SOC in treating acute viral respiratory infections in adults and children \geq 12 months old with SARI. The study will be conducted in up to 8 sites within Mexico, at sites that are part of the LaRed network. Subjects will be selected according to the inclusion and exclusion criteria listed below (Sections 4.3 and 4.4). The study is designed to enroll a total of 290 subjects who will be randomized in a 1:1 ratio. Enrollment will continue until 290 subjects are randomized, or March 2017, whichever comes first.

Prior to screening for inclusion in the study, informed consent (and assent for pediatric subjects as applicable) will be obtained. After completion of informed consent, screening for the study will occur. This involves review of the subjects' symptoms, medical conditions, physical exam, and pregnancy test for females able to become pregnant. All patients will initially be hospitalized. If the subject qualifies for the study, baseline assessments will occur including baseline vitals, safety labs, and nasopharyngeal swab or aspirate for PCR. Subjects will be randomized to a treatment kit and will begin treatment immediately. They will receive instruction on completion of their diaries, concomitant medications, and attending follow-up visits. Subjects will be followed on Study Days 3, 7, 14, and 28. The subject will be discharged from the hospital when clinically indicated as determined by the treating physician – follow-up visits may occur as inpatients or as outpatients.

On Study Days 3 (+/- 1) and 7 (+/- 1) a clinical assessment will be performed, diary cards collected, and safety labs will be obtained. Subjects that are hospitalized on Day 14 will have an in person visit. For subjects that are no longer hospitalized, the Day 14 visit may occur in person or by telephone. This visit is primarily for the collection of Day 7-14 diary card information. Study Day 28 will mark the end of study where subjects return for final clinical assessment, safety labs, and convalescent serologies.

Subjects that are still hospitalized after Study Day 28 will continue to be followed through the date of discharge.

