3.5 Definitions for the Purpose of this Study

Enrolled

For the purpose of collecting data and samples and reporting AEs, a subject will be considered enrolled beginning from the time the informed consent form is signed until the subject is considered “screen failure”, “discontinued”, or “completed”.

Randomized

Subjects are considered randomized when they meet all of the following criteria:

- Confirmation that the inclusion and exclusion criteria are met
- Consent is given and signed by the subject for the study
- Randomization number is assigned

Screen Failures

Subjects are considered screen failures when they meet 1 of the following criteria after signing consent:

- Screening tests reveal that the subject is ineligible
- Subject withdraws consent before being randomized

Discontinued

Subjects are considered discontinued when they meet 1 or more of the following criteria:

- Subject withdraws consent after being randomized (see Section 4.5)
- Subject is withdrawn after enrollment by investigator (see Section 4.7) including lost to follow-up

Completed

Subjects are considered completed when they are followed through Study Day 28 and complete the final study follow-up visit (Study Day 28) or die prior to this study visit.

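### Protocol 8.7.4 intends an automatic suspension of study drug, but its listed steps do not order one, let enrolment stay open during the review, use two clocks, and make DSMB review optional

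*Protocol*

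**What the plan says.** Protocol 8.7.4 sets two triggers. One is the same Grade 4 event or SAE in two or more subjects; the other is the same event of Grade 3 or higher in four or more. In each case the event must be unexpected and at least possibly related. The lead sentence gives the effect: "The following automatic pausing rules to suspend study drug administration are in place for this study".

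Two things are then listed as following a trigger:

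- a Medical Monitor review, "within 72 hours of being made aware of the events specified above";
- notice to the DSMB of that review and its findings.

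The next bullet covers a review not completed "within 72 hours of awareness by the Clinical Safety Office". In that case, "study enrollment will be halted until the review can take place". After the review, the sponsor, consulting the Medical Monitor, "may allow enrollment or ask the DSMB for a review of the safety data".

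Other sections bear on the same event:

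- **8.7.5:** the sponsor tells all sites that the study is paused. No deadline is given for that notice.
- **8.7.5.1:** the sponsor decides whether to resume or close in consultation with the Medical Monitor and the DSMB, for events that meet the stopping criteria. Sites inform their IRBs before study agent is given again.
- **8.7.7:** when pausing or halting criteria are met, the PI notifies the DSMB and obtains its recommendation on continuing, modifying or ending the study.
- **3.4:** "Subjects will be randomized to a treatment kit and will begin treatment immediately".

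**The concern.** A pausing rule has to be carried out within hours, by several parties, without interpretation. In 8.7.4 the stated purpose is to suspend drug, but the operative steps never instruct anyone to stop dosing. The only halt they name concerns enrolment, and it depends on a late review. A reader of those steps alone could conclude that recruitment goes on as normal for up to 72 hours.

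At stake is the safety of the few subjects on treatment, and of any who enter, after a serious unexpected related event has recurred. Elsewhere the protocol gives only partial cover. Section 4.6 stops drug for the affected subject only. The last bullet of 8.7.4 lets the sponsor pause at its discretion after routine aggregate analysis. Section 1.4.1 reports no drug-related SAEs in about 4,000 trial patients, so a trigger is probably rare, but 1.2.5 states that there are no data in hospitalized patients with influenza or other ILI.

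**Working it through.** This is first a comparison of texts. Arithmetic only shows the scale.

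**1. Is a dosing stop intended?** Yes. The lead sentence of 8.7.4, the pause notice in 8.7.5 and the resumption wording in 8.7.5.1 all presuppose one. No sentence says that dosing continues.

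**2. Do the listed steps deliver it?** No. They are a review and a notice. The conditional enrolment halt implies that enrolment stays open until the review is late. The sentence on what follows a study pause speaks of allowing enrolment, not of restarting drug.

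**3. Can open enrolment coexist with suspended drug?** Not comfortably. Section 3.4 has randomized subjects begin treatment immediately, and 6.2.1 wants the first dose within 24 hours. A subject entering early in a 72-hour review could not meet either while drug is held.

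**4. When does the 72-hour clock start?** One bullet counts from Medical Monitor awareness, the next from Clinical Safety Office awareness. The deadline and the enrolment halt tied to it may therefore fall at different times.

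**5. Is DSMB input needed before restart?** In 8.7.4 DSMB notice is mandatory but DSMB review is one of two options. In 8.7.7 a DSMB recommendation must be obtained. Section 8.7.5.1 also requires DSMB consultation, but only for events that meet the stopping criteria, so the mismatch rests mainly on 8.7.7.

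**6. Scale (illustrative).** Inputs: 290 subjects, 3-year accrual, 5 days of twice-daily dosing (10 doses each). Accrual confined to 6 or 4 months a year is my assumption and multiplies the rate by 2 or 3.

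- Subjects on treatment at once: 290 × 5 / (3 × 365.25) = 1.32; seasonal, 2.65 or 3.97. Half are on active drug.
- New subjects in 72 hours: 290 × 3 / 1,095.75 = 0.79; seasonal, 1.59 or 2.38.
- Doses in 72 hours: 72 / 12 = 6 of 10.
- Doses due within 72 hours for a subject at a random point of the course, with remaining time R uniform on 0 to 5 days: E[min(3, R)] = 9/10 + 3 × 2/5 = 2.1 days, or 4.2 doses.

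The documents do not give the probability of a trigger.

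**7. Cost of a hold.**

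- Doses missed in 72 hours: 1.32 × 4.2 = 5.6 to 3.97 × 4.2 = 16.7, of 2,900 planned (0.2% to 0.6%).
- Doses missed in a 5-day hold, which covers every remaining dose (5.0 on average): 1.32 × 5 = 6.6 to 3.97 × 5 = 19.9 (0.2% to 0.7%).
- Subjects not recruited in a 5-day hold: 1.3 to 4.0. This is a real loss only if the calendar date ends recruitment, since "Enrollment will continue until 290 subjects are randomized, or March 2017, whichever comes first".
- Power, using the protocol's unequal-variance t-test on log days (mean 7.7, variance 33.2, Delta 1.25). At the protocol's own N = 258 the unrounded moments give 79.0% against its stated 80%. The losses are:

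| Loss in a 5-day hold | All analysed | 10% dropout |
|---|---|---|
| None (N = 290) | 83.5% | 79.4% |
| 1.3 subjects | 83.3% | 79.2% |
| 4.0 subjects | 82.9% | 78.9% |

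**The case against.** The strongest defence is that the dosing stop is already stated. The lead sentence imposes it, the bullets merely describe the review that follows, and sites act on the sponsor's unconditional notice under 8.7.5. This largely stands as to intent. It also answers a stronger reading that a reader might infer: that the protocol has subjects stay on drug during the review, so that a subject could receive 6 doses, or all 10 if the review is late. That would require the sponsor and sites to disregard the lead sentence, 8.7.5 and 8.7.5.1 together. The documents do not support it as the planned course.

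A second defence is a two-tier scheme: drug is suspended at once and new consents stop only if the review is late. Section 3.5 lends it some support, since "a subject will be considered enrolled beginning from the time the informed consent form is signed", which precedes randomization and dosing. The scheme is possible, but 8.7.4 does not state it, and it does not explain why subjects should enter a trial whose drug is on hold.

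Third, a reader might infer that 8.7.4 removes the DSMB from the restart decision. It does not. DSMB notice is mandatory throughout, and nothing in 8.7.4 waives the PI's duty under 8.7.7. What remains is that the sponsor may reopen enrolment under one section without waiting for the recommendation that another requires.

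Finally, the Safety Review and Communications Plan and the DSMB monitoring plan are not available and may supply detail. They could settle the clock and the deadlines, but they would not remove conflicting protocol text.

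**Conclusion.** The point holds as a conflict within the safety instructions, not as a missing dosing stop. The intent to suspend drug is clear; the listed steps do not carry it out, and the enrolment clause cuts across it. The two clock starts are a smaller defect. The DSMB mismatch is real and rests mainly on 8.7.7.

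Confidence is high on the wording and lower on whether harm would follow, because that depends on how the sponsor and sites would act. The numbers are small and illustrative: roughly 1 to 4 subjects on treatment and 1 to 2 entering during a 72-hour review, with the upper figures resting on assumed seasonal accrual. The primary endpoint, its analysis and alpha are untouched. The change should be made because it protects subjects at almost no cost.

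**What to change.** Amend 8.7.4 in three places:

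1. When a criterion is met, dosing and new randomization stop at all sites upon immediate sponsor notice, until the review is complete. The stop of randomization is a deliberate addition to what the lead sentence covers.
2. Use one start for the 72-hour clock, for example awareness by the Clinical Safety Office.
3. Replace the choice between reopening enrolment and asking the DSMB with a sponsor decision made after the Medical Monitor's review and the DSMB recommendation, in line with 8.7.7 and 8.7.5.1. Leave any time limit for the DSMB to its monitoring plan.

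The cost is a clarifying amendment and a check that the Safety Review and Communications Plan and the DSMB monitoring plan agree with it. After a trigger, the few subjects on treatment may miss some of their remaining doses: about 6 to 17 in total for a 72-hour hold, or 7 to 20 for a 5-day hold. A few days of recruitment may be lost. If the March 2017 date binds, a 5-day hold lowers power by about 0.2 to 0.5 percentage points. Alpha is unchanged.

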8.7.5 Reporting a Pause

If a pausing requirement is met, a description of the adverse event(s) or safety issue must be reported by the Site Investigator by fax or email within one business day to the Sponsor CSO, PI, the IRB, and the DSMB.

The IND Sponsor will notify all sites that the study has been paused.

8.7.5.1 Review of Pauses and Resuming Rules

The site IRB/IECs will be notified by the site PI of any study pause, and the DSMB will be notified by the study chair of any study pause. The IND Sponsor, in consultation with the Sponsor's Medical Monitor and the DSMB, will conduct the review and make the decision to

resume or close the study for events that meet the criteria for stopping the study. As part of the review, the reviewers will also advise on whether the study needs to be paused again for any subsequent event of the same type. The IND Sponsor will notify the Site Investigators of this decision. The Site Investigators will notify their local IRB(s) of the decision to resume administration of the study agent prior to resumption.

The reviewing IRB/IEC has the right to pause enrollment at the sites it is responsible for at any time.

8.7.6 Safety Review and Communications Plan (SRCP)

A Safety Review and Communication Plan (SRCP) has been developed for the protocol. The SRCP is an internal communications document which delineates the safety oversight responsibilities of the Protocol chairs, the CSO, and other stakeholders. The SRCP also includes the overall plan for conducting periodic safety surveillance assessments.

8.7.7 Data and Safety Monitoring Board

The DSMB will review and approve a detailed DSMB monitoring plan before the study commences. The Board will review the study per the monitoring plan, but as long as subjects are enrolled into the study, the Board will review the study at least annually, and may convene additional reviews as necessary. The Board will review the study data to evaluate the safety, efficacy, study progress, and conduct of the study. All SAEs, all unanticipated problems, and all IND Safety Reports will be reported by the PI to the DSMB at the same time they are submitted to the IRB or IND Sponsor. The PI will notify the DSMB of any cases of intentional or unintentional unblinding as soon as possible. The PI will notify the Board at the time pausing or halting criteria are met and obtain a recommendation concerning continuation, modification, or termination of the study. The PI will submit the written DSMB summary reports with recommendations to the IRB(s).

The DSMB will review study-related data at the following intervals:

- Before enrollment
- Periodic safety review during the study, at least twice a year

These reviews may contain data that have not been monitored and therefore not verified against the source documents. Details of the review will be provided in the DSMB monitoring plan. A copy of the randomization codes will be provided to the DSMB executive secretary in a sealed envelope in case the DSMB requires this information to make its recommendation.

